7.4.2.7 STOMATITIS AND MUCOSITIS

Preventive measures may include a comprehensive oral examination to identify and treat any potential risk for complications before study treatment is initiated. Appropriate correction of local factors should be instituted as indicated, such as modification of ill-fitting dentures and appropriate care of gingivitis.

During treatment with cabozantinib, good oral hygiene and standard local treatments such as non-traumatic and non-irritating cleansing, and oral rinses (e.g., with a weak solution of salt and baking soda) should be maintained. Lips should be kept moisturized with lip balm. The use of lipstick, lip-gloss, and Vaseline should be avoided.

Local treatment should be instituted at the earliest onset of symptoms. Obtain bacterial/viral culture if oral infection is suspected and treat infection as clinically indicated.

7.4.2.8 SKIN AND SUBCUTANEOUS TISSUE DISORDERS

Wound healing and surgery: Cabozantinib has the potential to cause wound healing complications and wound dehiscence which may even occur long after a wound has been considered healed. Therefore, surgical and traumatic wounds must not only be completely healed prior to starting cabozantinib treatment but must also be monitored for wound dehiscence, wound infection and other signs of impaired wound healing while the subject is being treated with cabozantinib. If dehiscence occurs, cabozantinib treatment should not be restarted until complete healing has taken place.

Palmar-plantar erythrodysesthesia syndrome (PPES; also known as hand-foot syndrome), skin rash (including blister, erythematous rash, macular rash, skin exfoliation, dermatitis acneiform, and papular rash), pruritus, dry skin, erythema, pigmentary changes, and alopecia have been reported with cabozantinib. All subjects on study should be advised on prophylactic measures including the use of emollients, removal of calluses, avoidance of exposure of hands and feet to hot water leading to vasodilatation, protection of pressure-sensitive areas of hands and feet, and use of cotton gloves and socks to prevent injury and keep the palms and soles dry.

Early manifestations include tingling, numbness, mild hyperkeratosis, and symmetrical red and swollen areas on the palms and soles. The lateral sides of the fingers or periungual zones may also be affected. Adequate interventions are required to prevent worsening of skin symptoms such as blisters, desquamations, ulcerations, or necrosis of affected areas. Analgesics may be required for pain control.

Aggressive management of symptoms is recommended, including early dermatology referral. Treatment recommendations in response to PPES are summarized in **Table 7-6**.

Table 7-6: Management of Hand-Foot Syndrome (PPES) Associated with Cabozantinib

CTCAE v.5.0 Grade	Action To Be Taken
Grade 1	Cabozantinib treatment may be continued at the current dose if PPES is clinically insignificant and tolerable. Otherwise, cabozantinib should be reduced to the next lower dose level. ^a Start urea 20% cream twice daily AND clobetasol 0.05% cream once daily. Reassess at least weekly; if PPES worsens at any time or does not improve after 2 weeks, proceed to the intervention guidelines for Grade 2.
Grade 2	Cabozantinib treatment may be continued if PPES is tolerated. Cabozantinib should be dose reduced or interrupted if PPES is intolerable. Continue urea 20% cream twice daily AND high potency steroid cream (e.g., clobetasol 0.05%) once daily and add analgesics (e.g., NSAIDs/gamma-aminobutyric acid agonists) for pain control if needed. Reassess at least weekly; if PPES worsens or affects self-care, proceed to the intervention guidelines for Grade 3.
Grade 3	Interrupt cabozantinib treatment until severity decreases to Grade 1 or 0. Continue treatment of skin reaction with high potency steroid cream (e.g., clobetasol 0.05%) twice daily AND analgesics. Resume study drug at a reduced dose if PPES recovers to Grade ≤ 1. Discontinue subject from study treatment if PPES does not improve within 6 weeks.

CTCAE, Common Terminology Criteria for Adverse Events; NSAID, non-steroidal anti-inflammatory drug; PPES, palmar plantar erythrodysesthesia syndrome.

^a Permitted dose levels are defined by individual protocols.

7.4.2.9 OSTEONECROSIS

Osteonecrosis has been reported in subjects treated with cabozantinib. Additional risk factors include use of bisphosphonates and denosumab, chemotherapy and anti-angiogenic drugs, use of corticosteroids, local radiotherapy, and dental or orofacial surgery procedures.

Osteonecrosis of the jaw (ONJ) can manifest as jaw pain, osteomyelitis, osteitis, bone erosion, tooth or periodontal infection, toothache, gingival ulceration, or gingival erosion. Persistent pain or slow healing of the mouth or jaw after dental surgery may also be manifestations of osteonecrosis.

Advise subjects regarding oral hygiene practice and to quickly report symptoms to investigator. Caution should be used in subjects receiving bisphosphonates.

Invasive dental procedures should be avoided. In cases where dental procedures are unavoidable, treatment with cabozantinib should be interrupted for at least 4 weeks prior to the procedure and resumed after complete wound healing has occurred. Bone healing may often require a protracted time.

Cabozantinib will be permanently be discontinued in subjects who develop osteonecrosis of the jaw.

7.4.2.10 PROTEINURIA

Proteinuria has been reported with cabozantinib. Proteinuria should be monitored by measuring UPCR. **Table 7-7** provides treatment guidelines for proteinuria deemed related to cabozantinib.

Cabozantinib should be discontinued in subjects who develop nephrotic syndrome (proteinuria > 3.5 grams per day in combination with low blood protein levels, high cholesterol levels, high triglyceride levels, and edema).

Table 7-7: Management of Proteinuria Associated with Cabozantinib

Severity of Proteinuria (UPCR)	Management of Proteinuria
≤ 1 mg/mg (≤ 113.1 mg/mmol)	
 No change in cabozantinib treatment or monitoring
> 1 and < 3.5 mg/mg (> 113.1 and < 395.9 mg/mmol)	
 Consider confirming with a 24-h protein assessment within 7 days No change in cabozantinib treatment required if UPCR ≤ 2 mg/mg or urine protein ≤ 2 g/24 h on 24-h urine collection. Dose reduce or interrupt cabozantinib treatment if UPCR > 2 mg/mg on repeat UPCR testing or urine protein > 2 g/24 h on 24-h urine collection. Continue cabozantinib on a reduced dose if UPCR decreases to < 2 mg/mg. Consider interrupting cabozantinib treatment if UPCR remains > 2 mg/mg despite a dose reduction until UPCR decreases to < 2 mg/mg. Restart cabozantinib treatment at a reduced dose after a dose interruption. Repeat UPCR within 7 days and once per week. If UPCR < 1 mg/mg on 2 consecutive readings, UPCR monitoring can revert to protocol-specific times. (Second reading is confirmatory and can be done within 1 week of first reading.) If UPCR remains > 1 mg/mg and < 2 mg/mg for 1 month or is determined to be stable (< 20% change) for 1 month, check urine protein/creatinine per protocol or as clinically indicated.
≥ 3.5 mg/mg (≥ 395.9 mg/mmol)	
 Interrupt cabozantinib treatment pending repeat UPCR within 7 days and/or 24-h urine protein. If ≥ 3.5 mg/mg on repeat UPCR, continue to interrupt cabozantinib treatment and check UPCR every 7 days. If UPCR decreases to < 2 mg/mg, restart cabozantinib treatment at a reduced dose and monitoring of urine protein/creatinine should continue weekly until the UPCR decreases to < 1 mg/mg. If UPCR remains > 1 mg/mg and < 2 mg/mg for 1 month or is determined to be stable (< 20% change) for 1 month, check urine protein/creatinine per protocol or as clinically indicated.
Nephrotic syndrome	
 Discontinue cabozantinib treatment

RCC, renal cell carcinoma; UC, urothelial carcinoma; UPCR, urine protein/creatinine ratio.

7.4.2.11 NERVOUS SYSTEM DISORDERS

Cabozantinib appears to represent minimal risk of adverse neurological effects based on nonclinical Good Laboratory Practice (GLP)-compliant toxicology studies. Dysphonia, dysgeusia, headache, dizziness, confusional state, convulsion, depression, memory impairment, hypoesthesia, peripheral neuropathy, insomnia, ataxia, and encephalopathy have been observed in clinical studies with cabozantinib. The development of any new or progressive, unexplained neurological symptoms should be assessed for underlying causes.

RPLS has been reported. RPLS should be considered in any subject presenting with seizures, headache, visual disturbances, confusion or altered mental function. Cabozantinib treatment should be discontinued in subjects with RPLS.

7.4.2.12 HEPATOCELLULAR TOXICITY

Elevation of aminotransferases (ALT and AST): Evaluation of subjects with elevated transaminases or bilirubin should be individualized and guided by the presence of specific risk factors such as liver conditions (e.g., liver cirrhosis, metastases to the liver, thrombosis of portal or hepatic vein, hepatocellular carcinoma, hepatitis), concomitant hepatotoxic medication, alcohol consumption, and cancer related causes.

Cabozantinib should be interrupted for related CTCAE Grade 3 or higher hepatic injury (transaminase increase to $> 5 \times \text{ULN}$) and when transaminase increases are accompanied by progressive elevations of total bilirubin, and/or elevations of coagulation tests (e.g., International Normalized Ratio [INR]). More frequent monitoring of transaminases should be considered and cabozantinib should be interrupted until the etiology of the abnormalities is determined and these abnormalities are corrected or stabilize at clinically acceptable levels. Cabozantinib should be discontinued if hepatic dysfunction is not reversed despite interruption of study treatment. Elevations of aminotransferases when hepatic metastases are present may not require dose modifications if there are no progressive changes in the aminotransferases (less than a doubling) and if there are no progressive elevations in serum bilirubin concentration or coagulation factors. Elevations $>3 \times \text{ULN}$ of ALT or AST concurrent with $>2 \times \text{ULN}$ total bilirubin without other explanation (such as initial findings of cholestasis and obstructive disease, viral hepatitis, pre-existing or acute liver disease, or another drug capable of causing the observed injury) can indicate drug-induced liver injury (DILI). Study drug should be permanently discontinued in cases determined to be DILI according to Hy's Law review.

7.4.2.13 INFECTIONS AND INFESTATIONS

Infections are commonly observed in cancer subjects. Predisposing risk factor include a decreased immune status (e.g., after myelosuppressive anticancer therapies, splenectomy), destructive growth of the underlying malignancy including bone marrow infiltration with suppression of normal hematopoiesis, as well as the presence of IV devices.

Infections and abscesses should be treated with appropriate local care and systemic therapy. Cabozantinib should be interrupted until adequate healing has taken place.

7.4.2.14 BLOOD AND LYMPHATIC SYSTEM DISORDERS

Hematological toxicities (i.e., neutropenia and thrombocytopenia) and associated complications have been observed after administration of cabozantinib and may be managed with dose interruptions

and/or dose reductions. Subjects with hematologic toxicities may require additional or more frequent laboratory tests according to institutional guidelines.

Dose reductions or dose interruptions for hematological toxicities are not mandated but can be applied as clinically indicated. Supportive care for thrombocytopenia or anemia, such as transfusions, may be managed according to institutional guidelines. The use of colony-stimulating growth factors should be considered. Febrile neutropenia or evidence of infection associated with neutropenia must be assessed immediately and treated appropriately and in a timely manner according to institutional guidelines.

7.4.2.15 FATIGUE

Common causes of fatigue, such as anemia, deconditioning, emotional distress (depression and/or anxiety), poor nutrition, dehydration, sleep disturbance, and hypothyroidism should be ruled out and treated according to standard of care. Pharmacological management should be considered after disease specific morbidities have been excluded when not prohibited.

7.4.2.16 WEIGHT LOSS

Anorexia and weight loss should be managed according to local standard of care including nutritional support. Pharmacologic therapy should be considered for appetite enhancement when not prohibited by a particular protocol.

7.4.2.17 CORRECTED QT PROLONGATION

The effect of orally administered cabozantinib 140 mg qd on QTc interval was evaluated in a placebo-controlled study in subjects with MTC. A mean increase in QTcF of 10-15 ms was observed after 4 weeks after initiating cabozantinib treatment. A concentration-QTc relationship could not be definitively established. Changes in cardiac wave form morphology or new rhythms were not observed. No cabozantinib-treated subjects in this study had a QTcF > 500 ms. Review of the larger safety database (~5000 subjects exposed to cabozantinib in clinical trials and in post-marketing experience) confirmed the absence of safety concerns associated with QT prolongation. There were no events of torsades de pointes reported.

Concomitant treatment with strong cytochrome P450 (CYP) 3A4 inhibitors, which may increase cabozantinib plasma concentrations, should be avoided.

If at any time on study there is an increase in QTcF to an absolute value > 500 ms, two additional ECGs must be performed with intervals not less than 3 min apart within 30 min after the initial ECG.

If the average QTcF from the three ECGs is > 500 ms, the following actions must be taken:

- Interrupt cabozantinib treatment
- Hospitalize symptomatic subjects (e.g., with palpitations, dizziness, syncope, orthostatic hypotension, a significant ventricular arrhythmia on ECG) for a thorough cardiology evaluation and management
- Consider cardiology consultation for asymptomatic subjects for evaluation and management
- Check electrolytes, especially magnesium, potassium and calcium; correct abnormalities as clinically indicated

- Check concomitant medications for any medication that may have contributed to QT prolongation, and if possible, discontinue these medications (<http://www.qtdrugs.org>)
- Repeat ECG triplicates hourly until the average QTcF is ≤ 500 msec, or otherwise determined by consultation with a cardiologist or appropriate expert.

Subjects with QTc prolongation and symptoms must be monitored closely until the QTc elevation and symptoms have resolved. Cabozantinib treatment may be restarted at a reduced dose level if all of the following conditions are met:

- Symptoms are determined to be unrelated to the QT interval prolongation
- The QTcF value > 500 ms is not confirmed
- Cabozantinib treatment has been interrupted through a minimum of 1 week following the return of the QTcF to ≤ 500 ms.
- QT prolongation can be unequivocally associated with an event other than cabozantinib administration and is treatable/has been resolved

Following reinitiation of study treatment, ECGs must be repeated weekly for 2 weeks, then every 2 weeks for 1 month, then according to the protocol-defined time points.

Cabozantinib treatment must be permanently discontinued if either of the following applies:

- Cardiac evaluation confirms that symptoms are the consequence of QT interval prolongation
- Recurrence of QTcF prolongation after reinitiation of study treatment at a reduced dose

7.4.2.18 ELECTROLYTE DISORDERS

Serum electrolyte disorders including hyponatremia, hypokalemia, hypomagnesemia, and hypophosphatemia have been reported during treatment with cabozantinib, and serum electrolyte levels should be monitored frequently while receiving cabozantinib. Clinically relevant electrolyte disorders should be managed according to the dose modification guidelines as outlined in Section 7.3 or as clinically indicated. Standard clinical practice guidelines should be used for management of electrolyte disorders and may include oral or intravenous replacement.

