5 TARGET POPULATION

5.1 INCLUSION CRITERIA

1. Male, age ≥ 18 years old.
2. Karnofsky Performance Status (KPS) of ≥ 70 .
3. Histologic evidence of adenocarcinoma of the prostate who are deemed candidates for curative radical prostatectomy.
4. Planned robotic or laparoscopic prostatectomy technique.
5. Low risk for conversion to open prostatectomy, in the opinion of the treating surgeon.
6. Intermediate-high or high risk, clinically localized disease by the following criteria:
 - Prostate cancer in at least 2 cores with a Gleason score ≥ 7 (4+3 or 3+4) in at least 1 of those cores.
 - No definite evidence of metastasis, in the opinion of the investigator.
7. Adequate organ function as defined by the following criteria within 14 days prior to first dose of study treatment:
 - Aspartate transaminase (AST) and alanine transaminase (ALT) ≤ 3 x local laboratory upper limit of normal (ULN)
 - Total serum bilirubin ≤ 1.5 x ULN, (for subjects with Gilbert's disease ≤ 3 x ULN)
 - Absolute neutrophil count (ANC) ≥ 1500 /L without granulocyte colony-stimulating factor support.
 - White blood cell count ≥ 2500 /mm³
 - Serum albumin ≥ 2.8 g/dl
 - Platelets $\geq 100,000$ /mm³
 - Hemoglobin ≥ 9.0 g/dL
 - Serum calcium ≤ 12.0 mg/dL
 - Serum creatinine ≤ 2.0 x ULN or calculated creatinine clearance ≥ 30 mL/min.
 - Urine protein/creatinine ratio (UPCR) ≤ 1 mg/mg (≤ 113.2 mg/mmol).
8. Written Authorization for Use and Release of Health and Research Study Information (HIPAA authorization per institutional requirements)
9. Evidence of a personally signed and dated informed consent document indicating that the subject has been informed of all pertinent aspects of the trial.
10. Willing/able to adhere to the prohibitions and restrictions specified in this protocol.
11. Agrees to use a condom (even men with vasectomies) and another effective method of birth control if subject is having sex with a woman who is pregnant or a woman of childbearing potential while on study drug and for 4 months following the last dose of study drug.

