5. Day 1 physical exam and KPS do not have to be repeated if screening physical exam and KPS were performed within 7 days prior to Day 1 visit. Vitals signs must be completed on Day 1 regardless of when they were collected during screening.
6. Randomization may take place any time before or on day 1, after the patient is confirmed to be eligible.
7. Cabozantinib will be administered at 40 mg daily for 28 days. A pill diary will be provided to the subject. Study drug will be dispensed directly from the clinic. Unused drug will be returned to the clinic.
8. Prostatectomy will occur 2 weeks (14 + 3 days) after the last dose of cabozantinib. Tissue will be procured for pathologic, molecular, and immunologic assessments.
9. Relapse free survival follow up may be captured over the telephone, clinic visit or chart review every 3 months +/- 1 month.
10. Laboratory assessments at the times indicated include:
 - Complete blood count (CBC) with differential
 - Serum chemistries (CMP): Sodium, Potassium, Chloride, Bicarbonate, blood urea nitrogen (BUN), Creatinine, Glucose, aspartate aminotransferase (AST), alanine aminotransferase (ALT), total bilirubin, alkaline phosphatase, and LDH.
 - Coagulation Factors: PT/INR or PTT will be drawn at baseline only.
 - PSA
 - Testosterone
 - Thyroid function testing: Will include TSH and T4.
 - Urine Protein Creatinine Ratio: $UPCR = (\text{Urine protein mg/dl}) / (\text{urine creatinine mg/dl}) = \text{numerically equivalent to gm protein excreted in urine over 24 hours.}$
 - Notes:** Screening labs (except testosterone) must be completed within 7 days of day 1, or they must be repeated on day 1.
11. CBC with differential, CMP, coagulation factors and urine protein creatinine ratio must be completed within 14 days of Day 1 if subject is assigned or randomized to Arm A: Cabozantinib.
12. Thyroid function tests (TFTs) will be repeated at the safety follow up visit in those who require clinical intervention due to alteration in TFTs at an earlier time point.
13. Immune and androgen correlates will only be collected at baseline and on Day 29.
14. For extraordinary responders (i.e. pCRs) we will obtain archival tissue from their pre-prostatectomy prostate biopsy if available.

FIGURE 3: SCHEDULE OF EVENTS

Arm B: Immediate Prostatectomy

Assessment	Screening	Day	Relapse free Follow up
	D-42 to -1	1 ¹	3 year follow up (from prostatectomy)
Informed Consent	X		
Medical History and Demographics	X		
Interval history ²		X	

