6.3 SCREENING- BOTH ARMS

The screening examination will take place within 42 days of initiation of therapy or surgery. An informed consent form must be signed by the subject before any study-specific screening procedure takes place.

Subject data to be collected at the Screening Examination includes:

- Informed consent process utilizing a signed and dated IRB-approved ICF
- Confirmation of inclusion/exclusion criteria

- Medical history including concomitant illnesses and oncologic history. Oncologic history must include specific documentation of prostate cancer histologic diagnosis.
- Prior and concomitant medications and non-pharmacologic treatments taken within 4 weeks of screening will be recorded.
- ECG
- Sample collection for the following laboratory evaluations (all standard-of-care except PT/INR and PTT):
 - Complete blood count (CBC) with differential: WBC count with differential, platelet count, hemoglobin, and hematocrit.
 - Serum chemistries: Sodium, potassium, chloride, blood urea nitrogen (BUN) or urea, creatinine, glucose, carbon dioxide (CO₂) or bicarbonate, aspartate aminotransferase (AST), alanine aminotransferase (ALT), albumin, total bilirubin, alkaline phosphatase, LDH.
 - Urine protein creatinine ratio
 - Testosterone and PSA levels.
 - Prothrombin time (PT)/INR or partial thromboplastin time (PTT) test.
- Correlative samples will be drawn at screening. See lab manual for details.
- Physical examination to be conducted and height (cm), weight (kg), and vital signs (including temperature [°C], blood pressure [mmHg], heart rate [beats per minute], respiratory rate [breaths per minute]). Height will be collected at screening only.
- Karnofsky Performance Status (KPS)

Once the subject completes the screening examinations and is determined to be eligible, he will be assigned or randomized to arm A or arm B and enrolled.

Arm A

- Cabozantinib will be administered orally at 40 mg daily for 28 days
- 14 day + 3 days washout prior to prostatectomy
- Prostatectomy

Arm B

- Immediate prostatectomy

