6.7 TREATMENT PERIOD

6.8 DAY 1 - ARM A ONLY

The following must be performed on Day 1 prior to dose of cabozantinib:

- Interval history
- Physical examination including major body systems. The Day 1 physical examination does not need to be performed if the screening physical examination was performed within 7 days of the Day 1 visit.
- Karnofsky Performance Status (KPS), body weight, and vital signs (temperature, blood pressure, heart rate, respiratory rate). The Day 1 KPS evaluation does not need to be performed if the screening KPS evaluation was performed within 7 days of the Day 1 visit.
- Assessment of concomitant medications, toxicities and treatments
- Dispense study drug to the patient
- Sample collection for the following laboratory evaluations if not done for screening with 7 days:
 - Complete blood count (CBC) with differential: WBC count with differential, platelet count, hemoglobin, and hematocrit.
 - Serum chemistries: Sodium, potassium, chloride, blood urea nitrogen (BUN) or urea, creatinine, glucose, carbon dioxide (CO₂) or bicarbonate, aspartate aminotransferase (AST), alanine aminotransferase (ALT), albumin, total bilirubin, alkaline phosphatase, LDH.
 - Urine protein creatinine ratio
 - PSA level
 - Thyroid function testing: TSH and T4.

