7.4.2.1 CABOZANTINIB

The most frequent AEs experienced by $\geq 20\%$ of subjects treated with cabozantinib in descending order of frequency were diarrhea, fatigue, decreased appetite, nausea, weight decreased, PPES, vomiting, constipation, hypertension, dysgeusia, dysphonia, asthenia, and dyspnea. For a full description of the safety profile of cabozantinib, refer to the Cabozantinib Investigator's Brochure.

Other medically important but less frequent AEs including arterial thrombotic AEs (e.g., transient ischemic attack [TIA], and myocardial infarction [MI]) and venous thrombotic AEs (e.g., deep vein thrombosis [DVT] and pulmonary embolism), severe hemorrhagic events, proteinuria, wound healing complications, gastrointestinal (GI) perforation, abscesses including intra-abdominal and pelvic abscess, GI and non-GI fistula formation, osteonecrosis, and reversible posterior leukoencephalopathy syndrome (RPLS).

Adverse events associated with laboratory abnormalities experienced by $\geq 5\%$ of subjects treated with cabozantinib in descending order of frequency were anemia, AST increased, ALT increased, hypothyroidism, hypokalemia, hypomagnesemia, thrombocytopenia, hypocalcemia, hypophosphatemia, lactate dehydrogenase (LDH) increased, lipase increased, neutropenia, hyponatremia, ALP increased, leukopenia, and hyperglycemia.

Adverse events may occur within the first few weeks in the course of treatment with cabozantinib, as cabozantinib is expected to reach steady state exposure at approximately 2 weeks following first dose. Events that generally have an early onset include hypocalcemia, hypokalemia, thrombocytopenia, hypertension, PPES, abdominal pain, mucosal inflammation, constipation, diarrhea, and vomiting. Adverse events should be managed with supportive care at the earliest signs of toxicity. Dose reductions and treatment interruptions should be considered. Dose reductions are recommended for events that, if persistent, could become serious or intolerable (Section 7.3).

Cabozantinib should be discontinued for the following AEs: visceral perforation or fistula formation, severe hemorrhage, serious arterial thromboembolic events, nephrotic syndrome, hypertensive emergency, persistent uncontrolled hypertension despite optimal medical management, and RPLS.

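### Section 7.4.2.18 asks for frequent electrolyte monitoring on cabozantinib, but this is not fully carried into the visits: magnesium and phosphate are on neither the Day 15 nor the Day 29 list

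*Combined protocol and SAP*

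**What the plan says.** Section 7.4.2.18 (Electrolyte Disorders) names hyponatremia, hypokalemia, hypomagnesemia and hypophosphatemia, and in the same sentence states that "serum electrolyte levels should be monitored frequently while receiving cabozantinib". It gives no interval and no list of analytes, and it does not wait for a symptom. Clinically relevant disorders are then to be handled under the dose-modification guidelines.

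Section 7.4.2.1 lists laboratory-related adverse events seen in at least 5% of treated subjects. The list includes "hypokalemia, hypomagnesemia, thrombocytopenia, hypocalcemia, hypophosphatemia". The section adds: "Events that generally have an early onset include hypocalcemia, hypokalemia, thrombocytopenia".

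The chemistry panel is itemised in the Schedule of Events notes, which begin "Serum chemistries (CMP): Sodium, Potassium, Chloride, Bicarbonate, blood urea nitrogen (BUN), Creatinine, Glucose", and again visit by visit in sections 6.3, 6.8, 6.9, 6.10, 6.12 and 6.13, where the list begins "Serum chemistries: Sodium, potassium, chloride, blood urea nitrogen (BUN) or urea, creatinine, glucose". The rest of each list covers bicarbonate or CO2, liver tests and LDH, plus albumin in the visit sections only.

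Inclusion criterion 7 (section 5.1) reads "Adequate organ function as defined by the following criteria within 14 days prior to first dose of study treatment", and one of its limits is a serum calcium of at most 12.0 mg/dL.

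**The concern.** The protocol tells sites to watch electrolytes closely and names four disorders, then writes visit lists that test for two of them. A site that follows only those lists would not routinely measure magnesium or phosphate during the 28 days of drug. It could not apply the dose-modification guidance to a value it never obtained.

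Two things are at stake, both in Arm A. One is the safety of the treated men. The other is the completeness of exploratory endpoint 7 (adverse events by CTCAE v5.0), where a low count of these disorders could partly reflect an absence of testing.

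Calcium is a related but separate matter. It is an eligibility test that the screening list does not name, and hypocalcemia is described as an early event with no on-treatment calcium written down.

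**Working it through.** No power or sample-size figure is involved. The check is a comparison of texts and a count.

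**Step 1. The written chemistry lists.** There are eight.

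| Place | Timing relative to drug | Na, K | Mg, phosphate | Ca |
|---|---|---|---|---|
| 6.1, Arm A note 10 | covers all Arm A visits | yes | no | no |
| 6.1, Arm B note 7 | no drug | yes | no | no |
| 6.3 Screening | before drug | yes | no | no |
| 6.8 Day 1 | before first dose | yes | no | no |
| 6.9 Day 15 | on drug | yes | no | no |
| 6.10 Day 29 | end of dosing | yes | no | no |
| 6.12 Day 50 | 50 − 28 = 22 days after last dose | yes | no | no |
| 6.13 Safety visit, Day 57–85 | 29 to 57 days after last dose | yes | no | no |

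Alkaline phosphatase is an enzyme and is not counted as phosphate.

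**Step 2. The lists that bear on the guidance.** Section 7.4.2.18 concerns men while they take the drug. Of the eight lists, one is for the arm without drug, two are before the first dose and two are about three weeks or more after the last dose. Note 10 restates the Arm A visits. The visits that count are Day 15 and Day 29. Magnesium and phosphate are listed at 0 of these 2; sodium and potassium at 2 of 2. Disorders named in section 7.4.2.18: 4; with a scheduled analyte: 2; without: 4 − 2 = 2.

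**Step 3. Other routes to a test.**
- Section 7.4.2.17 asks for magnesium, potassium and calcium, but only once the average QTcF exceeds 500 ms. The Arm A schedule shows an ECG at screening only, so no scheduled on-treatment ECG would reveal that trigger.
- Section 7.4.2.2 asks for electrolyte monitoring in men with dehydration symptoms or risk factors, without naming analytes.
- Section 6.13 allows further tests as needed, but only at the safety visit, after the drug has stopped.

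Each is triggered by an event or falls off drug. None provides routine on-drug testing of all men.

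**Step 4. Calcium.** Criterion 7 sets limits on eleven measurements: AST, ALT, bilirubin, ANC, white cells, albumin, platelets, hemoglobin, calcium, creatinine and UPCR. Section 6.3 lists ten of them; calcium is the one missing.

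**Step 5. Size of the remedy.** One baseline plus Day 15 and Day 29 makes 3 time points, with 3 analytes each.
- 20 evaluable Arm A men: 20 × 3 × 3 = 180 assays.
- Section 11.1 allows up to 33 enrolled. If all the extra men are in Arm A: 33 − 10 = 23 men, and 23 × 3 × 3 = 207.
- Calcium at screening in both arms: up to 33. Upper total: 207 + 33 = 240.
- If the baseline is instead taken at screening in all 33 men, before allocation is known: 33 × 3 + 23 × 2 × 3 = 99 + 138 = 237, still below 240.

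These totals assume one magnesium and phosphate baseline per man and leave out screen failures, whose number the documents do not give.

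**The case against.** The strongest reply is that section 7.4.2.18 sets nothing the visits could breach. It is a recommendation with no interval or analyte list, in a section of management guidelines, much of which is general cabozantinib text: it discusses treated brain metastases, for example, in a trial that excludes metastatic disease. Sites remain free to order magnesium or phosphate on its authority. This stands: the point is a gap between guidance and schedule, not a contradiction. But an unspecific recommendation relies on the schedule for consistent practice, and more so with a second site planned.

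A reader might infer that the guidance is not carried into the visits at all, or might take 0 of 8 lists as the measure of the gap. The documents do not support either. Sodium and potassium are scheduled throughout, and only Day 15 and Day 29 bear on monitoring during treatment.

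A reader might also infer that calcium is never measured. Section 7.4.2.18 does not name calcium, criterion 7 already requires a value, and the panel is labelled CMP, so a local laboratory may report it. The lists are evidently not exhaustive, since albumin is in the visit sections but not in note 10. Calcium is therefore secondary. For magnesium and phosphate the documents offer no similar reason to expect a result.

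Finally, section 10.2.1 makes a laboratory value an adverse event only if it changes management or is clinically significant, so many mild values would go uncounted even if measured. That stands and limits the effect on endpoint 7.

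**Conclusion.** The point holds as a minor improvement to Arm A safety monitoring. Two of the four disorders named in section 7.4.2.18 have no scheduled test at either visit that matters, and calcium is missing from the screening list although eligibility depends on it.

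The conclusion assumes that sites test what the lists name and little more. Where local panels or habits go further, the gap is smaller. No number of missed cases can be given: the figure of at least 5% in section 7.4.2.1 comes without dose, duration or grade, and the documents give no rate for 28 days at 40 mg.

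A reader might go on to infer a biased comparison of adverse events between the arms, or a weakened stopping rule. Neither follows. Arm B has no scheduled toxicity assessment, so there is no such comparison to bias. The DLT definition, the stopping rules, the primary endpoint and its power do not depend on these analytes.

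**What to change.** 1. Add magnesium and phosphate, with calcium as a secondary item, to the Arm A chemistry at Day 15 and Day 29: in note 10 (marked for those visits) and in sections 6.9 and 6.10. Blood is already drawn at both.
2. Take one pre-dose baseline of the same analytes with the screening or Day 1 chemistry, whichever is drawn within 7 days of Day 1. Do not make a Day 1 sample compulsory. Section 6.8 opens its laboratory list with "Sample collection for the following laboratory evaluations if not done for screening with 7 days", and the entry "Thyroid function testing: TSH and T4" falls under that same waiver. A site that had tested thyroid function within 7 days might draw no blood on Day 1, and a compulsory sample would then mean a new draw.
3. List calcium in section 6.3, since criterion 7 needs it.

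The cost is roughly 180 to 240 add-on assays, a few more for screen failures, and the review of some incidental mild abnormalities. No extra visit or blood draw is required.
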